**Hospital Security Program for Engaging Communities with Firearm
Safe Storage Devices and Interventions: Data Collection Aim 2**

Study Protocol

January, 2024

Outline

1. Abstract
2. Overall objectives
3. Aims
 - 3.1 Primary outcome
 - 3.2 Secondary outcomes
4. Background
5. Study design
 - 5.1 Design
 - 5.2 Study duration
 - 5.3 Target population
 - 5.4 Accrual
 - 5.5 Key inclusion criteria
 - 5.6 Key exclusion criteria
6. Subject recruitment
7. Subject compensation
8. Study procedures
 - 8.1 Consent
 - 8.2 Procedures
9. Analysis plan
10. Human research protection
 - 10.1 Data confidentiality
 - 10.2 Subject confidentiality
 - 10.3 Subject privacy
 - 10.4 Data disclosure
 - 10.5 Data safety and monitoring
 - 10.6 Risk/benefit
 - 10.6.1 Potential study risks
 - 10.6.2 Potential study benefits
 - 10.6.3 Risk/benefit assessment

1. Abstract

To prevent workplace violence, in November 2021, Penn Medicine implemented the Evolv weapons detection system in Pennsylvania Hospital (1,2). For individuals who self-disclose they are carrying a weapon, or who are identified with weapon during screening, security guards offer the individual the option to leave with their weapon, or to place it in a safe, at the hospital, for storage. Security guards return the weapon when the patient or visitor is ready to leave. Beginning in July 2022 our team piloted a program in which security guards offer a cable lock and safety brochure when the gun owner returns to retrieve their firearm at the conclusion of their visit. To date, 47% of patients and visitors who stored their firearm with security have taken a cable lock when offered, resulting in over 300 firearm safety locks and brochures distributed to firearm owners. The Aims of this study are to: (1) Elucidate barriers and facilitators to implementing a hospital security screening firearm safety program through interviews with hospital security staff; (2) Design and pilot test a method for collecting data on storage device use among patients and visitors who accept firearm safety materials; (3) Conduct a pilot of distributing lockboxes and compare acceptance and usage rates to cable locks.

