8.2 Procedures

Study procedure. A unique QR code linking directly to the survey will be embedded into our firearm safety brochure and study poster available in the entry hall of PAH. Participants who scan positive for a firearm and are offered safety materials (inclusive of the brochure) will be informed that survey participation is optional, but that it is helpful to our efforts, and that participation will be compensated with a \$10 Amazon gift card for completing the initial survey and a \$20 Amazon gift card for completing the follow-up survey. Individuals who decline the device will also be eligible for the initial survey via the poster QR code. Gift cards will be distributed digitally via text in accordance with the participants consent to share their phone number. Only eligible participants will receive a text with a link to complete the optional follow-up survey.

Participants who self-select into the study via the study poster will be linked to the initial survey in Qualtrics with one re-worded question based on context. Individuals will receive \$10 Amazon gift card for completing the initial survey and a \$20 Amazon gift card for completing the follow-up survey. Only eligible participants will receive a text with a link to complete the optional follow-up survey.

Initial Survey via Brochure. Upon scanning the QR code on the brochure, an individual will be brought directly to the initial Qualtrics survey. The first question of the survey is a statement outlining that the individual's participation is voluntary and informed. The individual must select agree or disagree before proceeding with the survey. If the individual chooses to agree, they will then begin the initial survey. After completion of the survey, they will receive a text message with their Amazon giftcard information within 1-2 weeks. The text will read, "Hello, this is Penn Medicine. Thank you for participating in our survey. As an appreciation for your time, please see below for your gift card information: [INSERT GIFT CARD #]"

This initial survey will focus on the following elements. Survey language may be refined during the research process:

- 1.
2. To receive an Amazon gift card and participate in future follow-up surveys, please enter your phone number.
3. Most recent visit to Penn Medicine (mm/dd/yyyy)
4. Did you get a cable lock today?
 - a. Yes
 - b. No
5. [IF NO #3] What's the reason you didn't accept one?
 - a. Already have one
 - i. [LOGIC] How often do you use it?

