 1. Every time I store my device
 2. Almost every time I store my device
 3. Almost never when I store my device
 - ii. [LOGIC] What's your preference for storing your firearm? [text field]
 - b. Prefer different storage device
 - i. [LOGIC] Which of the following storage devices would you prefer?
 1. Lock box
 2. Trigger lock
 3. Gun safe
 4. Calmshell / "life jacket"
 5. Gun cabinet
 6. In-vehicle lock
 7. Other/key/PIN/biometric (please specify):
 - c. Don't want one
 - d. Not offered or not available
6. [IF YES #3] If you have accepted a device today, how likely are you to use it in the next week?
 - a. Extremely likely
 - b. Somewhat likely
 - c. Neither likely nor unlikely
 - d. Somewhat unlikely
 - e. Extremely unlikely
7. How do you usually store your firearm?
 - a. In a locked safe or gun cabinet
 - b. With a trigger lock or cable lock
 - c. Unlocked (not secured with a lock, in a locked container, or not stored in a locked cabinet)
 - d. Other (please specify)

Initial Survey via Poster. Upon scanning the QR code on the poster next to the distribution area, an individual will be brought directly to the initial Qualtrics survey. The first question of the survey is a statement outlining that the individual's participation is voluntary and informed. The individual must select agree or disagree before proceeding with the survey. If the individual chooses to agree, they will

then begin the initial survey. After completion of the survey, they will receive a text message with their Amazon giftcard information within 1-2 weeks. The text will read, "Hello, this is Penn Medicine. Thank you for participating in our survey. As an appreciation for your time, please see below for your gift card information: [INSERT GIFT CARD #]"

This initial survey will focus on the following elements. Survey language may be refined during the research process:

1. To receive an Amazon gift card and participate in future follow-up surveys, please enter your phone number.
2. Most recent visit to Penn Medicine (mm/dd/yyyy)
3. Are you interested in receiving a firearm storage device shipped to your address?
4. [IF NO #3] What's the reason you don't want one?
 - a. Already have one
 - i. [LOGIC] How often do you use it?
 1. Every time I store my device
 2. Almost every time I store my device
 3. Almost never when I store my device
 - ii. [LOGIC] What's your preference for storing your firearm? [text field]
 - b. Prefer different storage device

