2. Have you used the firearm storage device from Penn Medicine to secure your firearm? [Yes/No]
3. Have you made any other changes in your firearm storage? [write in]

Iterative Analysis and Refinement of Data Collection Methods: We will assess response rates every (1) week and tabulate responses on the acceptability of data collection methods. We will iteratively refine data collection methods over the course of 6 months to achieve the highest possible response rate. The participant data collected will be their phone number and/or their address for individuals completed the survey via the study poster. No identifying information or demographics will be collected to uphold anonymity. Cell phone number will be used to distribute the gift card via the Nudge Unit’s Google Voice account and re-contact with invitation to participate in the follow-up survey. Their address will only be used to ship the firearm storage device to individuals who self-enrolled in the study via the study posters.

9. Analysis plan

The primary outcome is survey response rate. This will be monitored via Qualtrics by looking at response volume by week. These responses will be compared to security department reports on the number of firearms identified/stored to allow us to calculate the proportion of eligible individuals who responded per week. The secondary outcome measures are: (1) firearm storage behavior among a) locked safe/gun cabinet, b) trigger lock or cable lock, c) unsecured, d) other (write in), (2) likelihood of using cable lock within the next week (extremely unlikely to extremely likely scale).

10. Human research protection

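### In the brochure channel, storage is first asked after the lock is handed over and without reference to the time before the visit, so before-after change may be understated among people who answer late

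*Protocol*

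**What the plan says.** The Abstract describes the handover: "security guards offer a cable lock and safety brochure when the gun owner returns to retrieve their firearm at the conclusion of their visit". The Background section repeats it. Lock and brochure are thus offered together, at the end of the visit.

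Section 8.2 gives the route into the brochure survey: "Upon scanning the QR code on the brochure, an individual will be brought directly to the initial Qualtrics survey". No time limit for completing it is stated. Two of its items presume completion on the day of the visit: "Did you get a cable lock today" (item 4) and "If you have accepted a device today, how likely are you to use it in the next week" (item 6). Item 7, the only question there on current storage that goes to everyone, is "How do you usually store your firearm". It has four answer categories, one of which is a trigger or cable lock.

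The follow-up survey, sent by text 1 month after enrollment, offers the same four categories but asks about storage since the visit, with the declared purpose of learning whether behavior changed. Its item 2 asks "Have you used the firearm storage device from Penn Medicine to secure your firearm", and its item 3 is a free-text question on other storage changes. Section 5.5 limits follow-up in the brochure channel to people who reported taking a cable lock.

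The form also asks for the date of the most recent visit. Section 10.1 says that Qualtrics records the time of completion, but restricts use of that information to screening for imposter participants.

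**The concern.** A before-after comparison needs a first measurement that describes behavior before the intervention. Here the first measurement always follows the offer of the lock and the safety material, and its wording does not direct the respondent back to the earlier period. A person who takes the brochure home, starts using the lock and answers some days later can truthfully choose the cable-lock category. At follow-up the same person chooses it again, and the pair shows no change although storage did change.

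Because follow-up is limited to people who reported taking the lock, every brochure participant with a complete pair is open to this. The people most affected are those who adopt the lock quickly. It is also not something analysis can repair: if storage before the visit is never asked, it cannot be reconstructed later. As section 10.1 stands, late answers could not even be identified by comparing completion time with visit date.

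**Working it through.** The protocol states no expected change, sample size or power for this outcome, so there is no figure to reproduce. The check sets the passages in order and then illustrates the possible size.

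**Order of events in the brochure channel**

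1. Lock and brochure are offered at firearm retrieval (Abstract; Background).
2. The survey is opened from the code on that brochure (8.2), so always after step 1, with no stated limit on the delay.
3. Item 7 asks about usual storage, with no reference to the time before the visit (8.2).
4. The follow-up asks about storage since the visit (8.2). For a late respondent this period already includes the moment at which item 7 was answered, so the two measurements overlap.

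In the poster channel, a person who asks for shipment answers the same item before the shipped device arrives, so the overlap does not arise from that device.

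**Illustration**

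Let p0 be the true share with secured storage before the visit, p1 the true share at follow-up, and c the share of the true change already reported in the initial survey.

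- Observed baseline = p0 + c × (p1 − p0)
- Observed change = (1 − c) × (p1 − p0)

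Inputs: p0 = 1/3 is an assumption suggested by the Background statement that two thirds of households with a firearm have at least one unlocked. That figure counts households, not an individual owner's usual storage. The values of p1 (0.50 to 0.70) and c (0 to 0.50) are assumptions with no source in the protocol.

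| c | p1 = 0.50 | p1 = 0.60 | p1 = 0.70 |
|---|---|---|---|
| 0 (true change) | 16.7 | 26.7 | 36.7 |
| 0.05 | 15.8 | 25.3 | 34.8 |
| 0.10 | 15.0 | 24.0 | 33.0 |
| 0.25 | 12.5 | 20.0 | 27.5 |
| 0.50 | 8.3 | 13.3 | 18.3 |

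(Observed change, percentage points.) Example: p1 = 0.60 and c = 0.25 give 0.75 × 26.7 = 20.0.

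The proportional loss is c itself. If late and prompt respondents adopt equally often, c = L × a, where L is the share answering late and a is the share of eventual adopters among them who already report the lock:

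- L = 0.10, a = 0.20: c = 0.02
- L = 0.20, a = 0.20: c = 0.04
- L = 0.20, a = 0.60: c = 0.12
- L = 0.40, a = 1.00: c = 0.40

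With same-day answers a is close to 0, and so is c.

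**A shift in the other direction**

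Safety material read before the question could make some owners judge their storage more strictly. If 5% or 10% of truly secured owners rated themselves unsecured at baseline, then with p1 = 0.60 and c = 0 the observed change would be 0.60 − 0.95/3 = 28.3 points or 0.60 − 0.90/3 = 30.0 points, against a true 26.7.

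**The case against.** The strongest reply is that the form expects same-day completion. Items 4 and 6 speak of today and treat use of the lock as still to come, and item 7 asks about habit. A lock received an hour earlier can hardly be someone's usual storage. This stands for prompt respondents, and it is why the bias cannot be taken as given. It does not settle the matter: the wording presumes promptness without enforcing it, item 7 lacks even the word *today*, and asking for a visit date allows for survey and visit falling on different days.

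Second, use of the device is asked directly at follow-up (item 2), and that answer does not depend on item 7. This also stands. Item 2 does not, however, show what the lock replaced: a user may have moved from unlocked storage or from a safe.

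Third, the study is a pilot of data collection with response rate as its primary outcome, the survey wording is declared provisional, and any before-after method may be set out in a statistical analysis plan. All true. This limits the weight of the point, but a question that was not asked cannot be supplied by an analysis plan.

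Two stronger readings are tempting. A reader might infer that the change is understated outright, perhaps by as much as 40%. That figure requires 40% late answers with every eventual adopter among them already using the lock, and the protocol supports neither input. A reader might also infer that a comparison of storage between brochure and poster participants is spoiled. The protocol plans to compare the channels on response rates only, and the two groups differ by design in any case.

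**Conclusion.** The point holds in a limited form. In the brochure channel the initial storage answer follows the device, has no completion window and is not tied to the time before the visit. Among people who answer late, before-after change in storage may therefore be understated, in proportion to how much of the change they already report. Among same-day respondents the effect is near zero. Its overall size, and even its net direction once a possible effect of the safety material is allowed for, cannot be derived from the protocol; the percentages above rest on assumed values. Follow-up item 2 is unaffected. This is a cheap improvement to a secondary outcome and no threat to the primary one.

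**What to change.** Reword brochure item 7 to: *Before the visit when you received this brochure, how did you usually store your firearm?* Use the same pre-visit anchor in the poster form, for consistency rather than to correct an error there.

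Optionally, amend section 10.1 so that the Qualtrics completion time may be used together with the reported visit date to identify late answers.

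The cost is one item in each form, which section 8.2 already allows to be refined, and slightly more reliance on recall over what is normally a short interval. The change takes the new lock out of the baseline answer if the item is answered accurately. It does not remove any effect that the safety material has on how people describe their earlier storage.

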3.3 Exploratory outcomes

To compare survey response rates between several different variations of survey distribution: web survey accessed via QR code posted in the entry hall; web survey accessed via QR code included on the safety brochure; follow-up survey link administered by text message.

4. Background

Firearm injury is the leading cause of death of children in the U.S. and Philadelphia (3). Our work shows unintentional injuries are the leading cause of nonfatal firearm injuries with rates disproportionately higher in Black communities (Figure 1). As in Philadelphia, forty percent of American adults live in a household with at least one firearm, and two thirds of these have at least one firearm that is unlocked (4–6). Secure storage of firearms can prevent youth suicide, unintentional injury, intimate partner homicide, theft, and violent crime (7–10). Education and legislation have had limited impact on promoting safe firearm storage (11–15).

[figure not shown]

Figure 1: Annual U.S. Firearm Injury Rates per 100,000 by Intent, Age, Race, and Ethnicity, 2019-20 (Kaufman...Delgado, under review)

Penn Medicine prohibits firearms within its buildings. In November 2021, Penn Medicine implemented the Evolv weapons detection system in entrances to Pennsylvania Hospital and its medical office buildings (2). In the first 5 months of the program, there were over 300,000 screening encounters and 408 firearms identified and stored by hospital security. In July 2022 our team piloted an innovative program in which security guards offer a firearm cable lock and safety brochure when the gun owner return to retrieve their firearm at the conclusion of their visit. To date, 47% of patients and visitors who stored their firearm with security have taken a cable lock when offered, resulting in over 300 firearm safety locks and brochures distributed to firearm owners.

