5.1 Design

Aim 2 of this research study is to design and pilot test a method for collecting data on storage device use among patients and visitors who accept firearm safety materials or are interested in receiving a firearm storage device shipped to their address. The study design is an iterative pilot test of survey data collection methods and determination of scalability and feasibility for distribution of firearm storage devices. The study population and sample will be (a) individuals who are patients or visitors to PAH who are screened

for a firearm, screen positive, and accept a firearm safety brochure and storage device OR (b) individuals interested in receiving a firearm storage device and self-scan the unique QR code on the study poster in the entry hall of PAH with minimal or no security supervisor engagement. A unique QR code linking directly to the initial survey will be embedded into the firearm safety brochure as well as the poster in the entry hall of PAH next to the distribution area. Individual group (a) will be informed by security that survey participation is optional, but that it is helpful for our efforts, and that participation will be compensated with a \$10 Amazon gift card for the initial survey and a \$20 Amazon gift card for completing the follow-up survey. Individual group (b) will not be actively engaged by security, and will self-enroll in the study by viewing the posted signage and completing the QR code linked survey. Individuals who decline the device will also be eligible for the initial survey via the poster QR code, but they will not be eligible for the follow-up survey.

The primary outcome measure is survey response rate: whether an eligible visitor or patient completed the firearm storage survey after accepting firearm safety materials or after scanning the QR code on the poster. This will be measured through Qualtrics survey completion rate and PAH Evolv security system foot traffic. We will use the survey completion rate as the numerator and the number of people scanning positive for a firearm as the denominator for this rate.

The secondary outcome measures are from initial and follow-up survey responses: (1) firearm storage behavior, (2) likelihood of using cable lock within the next week (extremely unlikely to extremely likely scale). These outcomes are directly tied to questions asked in both surveys.

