5.5 Key inclusion criteria

Individuals who are visitors or patients at Pennsylvania Hospital, are identified through the Evolv system as carrying a firearm, and who accept firearm safety materials OR any patient or visitor interested in receiving a firearm storage device who self-selects into the study by scanning the QR code on the study poster. For eligibility of the follow-up survey, participants must have responded yes to taking a cable lock

in the initial brochure survey or yes to receiving a firearm storage device shipped to their address from the poster survey.

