5.6 Key exclusion criteria

None.

6. Subject recruitment

Since this aim is a trial of data collection methods within an existing hospital program, individuals will not be recruited or enrolled individually, but instead eligible individuals will be offered the option to participate in the survey upon receipt of firearm safety materials or self-selection via scanning the QR code linked to the initial study survey. The former option will be presented to individuals alongside the existing distribution workflow of the program.

7. Subject compensation

Total potential compensation per participant is \$30 in the form of Amazon gift cards. Individuals will receive a \$10 Amazon gift card for completing the initial survey. If participants choose to complete the follow-up survey, they will receive a \$20 Amazon gift card. The gift card will be shared manually via text message with the participants within 1-2 weeks of survey completion. Participants who elect to have a firearm storage device shipped to their address will receive a free device (either a cable lock and/or lock box).

8. Study procedures

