 - i. [LOGIC] Which of the following storage devices would you prefer?
 1. Lock box
 2. Trigger lock
 3. Gun safe
 4. Calmshell / "life jacket"
 5. Gun cabinet
 6. In-vehicle lock
 7. Other/key/PIN/biometric (please specify):
 - c. Don't want to share my address
 - i. [LOGIC] Please select which of the following you'd be open to:
 1. Returning to Penn Medicine to pick up a free cable lock
 2. Receiving a free cable lock locally
 3. Other (please specify)
5. [IF YES #3] What is the best US shipping address for you?
 - a. [Text box fields for street, apt, city, zip, name]
6. How do you usually store your firearm?
 - a. In a locked safe or gun cabinet
 - b. With a trigger lock or cable lock
 - c. Unlocked (not secured with a lock, in a locked container, or not stored in a locked cabinet)
 - d. Other (please specify)
7. Once you receive your cable lock, how likely are you to use it in the next week?
 - a. Extremely likely

- b. Somewhat likely
- c. Neither likely nor unlikely
- d. Somewhat unlikely
- e. Extremely unlikely

Follow-up Survey: Participants who complete the initial survey and who agree to provide contact information will be contacted via text message 1 month after enrollment for a follow-up survey that adds questions about if and how participants have changed their storage behavior. The text language will read:

“Hello, this is Penn Medicine. Thank you for completing our initial survey. If you’re interested in taking the follow-up survey, please click the survey link below: [INSERT LINK]”

Participants will receive the second Amazon gift card incentive 1-2 weeks after completion of this survey. “Hello, this is Penn Medicine. Thank you for participating in our survey. As an appreciation for your time, please see below for your gift card information: [INSERT GIFT CARD #]”

The follow-up survey questions are subject to be amended based on the principal investigators’ discretion. Eligible participants from the initial survey, those who answered yes to accepting a cable lock, will be asked the following questions to understand if their behavior changed:

1. Since you’ve visited Penn Medicine, how have you stored your firearm? [option selection]
 - a. Participants select [a] in a locked safe or gun cabinet, b) with a trigger lock or cable lock, c) unlocked (not secured with a lock, in a locked container, or not stored in a locked cabinet), d) other (please specify) with an open comment box]

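### The poster survey never establishes that the respondent has a firearm, so the storage percentages of secondary outcome 1 can mix in people with none to store

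*Protocol*

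**What the plan says.** There are two ways into the survey. Under Section 5.5 of the protocol, the brochure route is for people whom the security screening has identified as carrying a firearm. The poster route is for "any patient or visitor interested in receiving a firearm storage device who self-selects into the study by scanning the QR code on the study poster". Section 5.6 lists no exclusions. Section 5.1 says that the poster group "will not be actively engaged by security, and will self-enroll in the study by viewing the posted signage and completing the QR code linked survey". Section 8.2 adds: "Individuals who decline the device will also be eligible for the initial survey via the poster QR code".

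Section 8.2 describes the poster version as the same initial survey with a single question changed to suit the setting. Its item 6 asks "How do you usually store your firearm", with no condition attached and four answers: locked safe or cabinet, trigger or cable lock, unlocked, and other with a write-in. Item 1 of the follow-up survey repeats these categories for storage since the visit. Under Section 5.5, poster respondents who ask for a device to be shipped are eligible for that follow-up.

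Section 9 defines the first secondary outcome on the same list: "firearm storage behavior among a) locked safe/gun cabinet, b) trigger lock or cable lock, c) unsecured, d) other (write in".

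**The concern.** On the brochure route the storage question is safe, because everyone who reaches it has just been found with a firearm. The poster route gives no such assurance, yet the question was carried over unchanged. A respondent without a firearm has to choose a storage practice that does not exist, skip the item if that is allowed, or explain under other.

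At stake is what the secondary outcome means. Section 2 presents the survey as a way to learn how firearm owners see storage. If some respondents have no firearm, the reported percentages describe a mixture of storage practice and the share of people with nothing to store. The follow-up wave has the same gap. Because only those who took or requested a device are followed, the share without a firearm may also differ between the two waves.

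This goes beyond an analysis detail that could be settled later. If a person without a firearm ticks one of the first three answers, no later rule can identify that person, because the information was never collected.

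**Working it through.** **Step 1. Does anything else in the protocol identify respondents without a firearm?**

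- Eligibility (Sections 5.3, 5.5, 5.6): interest in a device is required, a firearm is not.
- Contact with security (Section 5.1): none for the poster group.
- Poster item 3 asks about interest in a shipped device. The reasons offered to those who say no (item 4) are already having one, preferring another type, and not wanting to share an address. None of them means having no firearm.
- Imposter check (Section 10.1): it uses the number, time and location of completions. It does not test for a firearm.
- Poster item 6 and follow-up item 1: the only truthful outlet is the write-in under other, and other is itself an outcome category in Section 9.

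Nothing visible separates the two kinds of respondent, apart from a voluntary write-in.

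**Step 2. How far could the unlocked percentage move?**

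The protocol states no expected storage percentage for this outcome, so there is no figure to reproduce. Define:

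- p = share storing unlocked among respondents with a firearm (assumed)
- f = share without a firearm among all who answer the item (not in the protocol; assumed, 5% to 30%)
- q = share of those without a firearm who tick unlocked (unknown, 0 to 1)

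Observed unlocked share = p(1 − f) + qf, so the bias is f(q − p).

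With p = 50% and f = 20%:

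- q = 0: 0.50 × 0.80 = 40%
- q = 1: 0.50 × 0.80 + 0.20 = 60%

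Over the assumed range of f, for three values of p (lower figure q = 0, upper figure q = 1):

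| f | p = 1/3 | p = 1/2 | p = 2/3 |
|---|---|---|---|
| 5% | 31.7% to 36.7% | 47.5% to 52.5% | 63.3% to 68.3% |
| 10% | 30.0% to 40.0% | 45.0% to 55.0% | 60.0% to 70.0% |
| 20% | 26.7% to 46.7% | 40.0% to 60.0% | 53.3% to 73.3% |
| 30% | 23.3% to 53.3% | 35.0% to 65.0% | 46.7% to 76.7% |

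The width of each interval equals f. The bias vanishes if f = 0, if those without a firearm skip the item or are removed, or if q happens to equal p.

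**Step 3. Pooling with the brochure route.** Here f refers to whatever set is in the denominator. If half of the pooled respondents came by poster and 20% of those had no firearm (both assumed), f would be 0.5 × 20% = 10%, and the p = 1/2 range would narrow to 45% to 55%.

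**The case against.** Several points on the other side are sound.

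- **The poster route is not open to everyone.** It is for people interested in a storage device, which should favour those who have a firearm or access to one. Interest is only loosely enforced, since the survey has a branch for people who do not want a device and decliners may enter. Still, poster respondents are not the general public.
- **The write-in helps.** Someone who writes under other that there is no firearm can be recoded. This recovers only those who write it.
- **The instrument is provisional.** Section 8.2 allows survey wording to be refined, and the study is an iterative pilot. That makes the change easy, but no firearm question is among the planned items.
- **Some text could not be checked.** The consent statement and the wording of the poster were not available, and either might address firearm owners. The eligibility criteria and listed items do not.
- **Denominators and coding rules are commonly left to an analysis plan.** Their absence from Section 9 is not the complaint. The complaint is that the survey does not collect what such a rule would need.

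Three stronger readings are tempting and should be resisted.

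- A reader might infer that most poster respondents have no firearm. Section 4 reports 408 firearms in over 300,000 screenings (408/300,000 = 0.136%) and says that "forty percent of American adults live in a household with at least one firearm", which leaves 60% who do not. The first figure counts encounters and carrying into a hospital, not people and ownership. The second is national. Neither describes people who choose to scan a poster about storage devices.
- A reader might infer that a poster-versus-brochure comparison of storage would be spoiled. No such comparison is planned; the comparison by route in Section 3.3 concerns response rates.
- A reader might infer that device use at follow-up is falsified. Device use is not a listed secondary outcome, and someone who received a device and did not use it is correctly a non-user from the distribution programme's point of view.

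**Conclusion.** The point holds as a flaw in data collection. The poster route does not require or record a firearm, the storage item presumes one at both waves, and the outcome categories have no place for a respondent without one. The size is unknown because f and q are unknown, and the direction is not fixed: reading the problem as simple dilution assumes that nobody without a firearm ticks unlocked. The 40% to 60% range is an illustration that rests on the assumed p = 50% and f = 20%, not an estimate. If few people without a firearm respond, the effect is small. The outcome affected is secondary and descriptive; the primary outcome, survey response rate, does not depend on this item. The correction is worth making because it is cheap and because ticked answers cannot be repaired afterwards.

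**What to change.** 1. Add one answer to poster item 6 and to follow-up item 1, to the effect of: *I do not have or store a firearm*. Wording that covers having or storing keeps in people who look after a household firearm that they do not own.
2. Report how many choose it, by entry route and by wave.
3. State in Section 9 that storage percentages are computed among respondents who report a firearm.
4. If device use at follow-up is reported, show it both for all recipients and for those who report a firearm.

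The cost is one answer option in two surveys and one or two sentences in Section 9. No new identifier is collected, so the confidentiality aim is not affected in that respect. There is a small downside: a wary owner may choose the new answer and drop out of the denominator. Reporting its count shows how many respondents that could concern. The option works only for responses collected after it is added, so earlier responses, if any, should be reported separately.
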